8.6 Analyses

Aim one anticipated results: We hypothesize at least 0.25 log reductions in the HIV reservoir at month 12 in study participants who have a demonstrated anti-proliferative response to MMF treatment. We hypothesize that cell-associated HIV DNA will undergo a shift from predominantly residing in T_{CM} and T_{EM} to predominantly residing in T_N and T_{SCM}. Further, we predict that reservoir depletion will occur with equivalent rates in blood, and GALT.

We will compute the change in reservoir volume in two ways. First, descriptively, we will use individual linear regressions to compute a slope in log viral load (**VL**) for each participant using time as the only covariate; and then we will describe the mean and standard deviation of that slope. Secondly, we will use linear mixed effects models, as others have done,^{60,61} to estimate an average slope using all the data at once, and a random intercept and slope per person. Estimation of a fixed effect for the interaction of time with treatment arm will help us determine whether the reservoir decreases more quickly with ART+MMF than with ART only in historical controls. We will assess the changing composition of the reservoir using similar models and include the proportion of cells that are naive (T_N) as the outcome in a generalized linear mixed model with a log link. An interaction of time by treatment arm will determine whether rate of change in composition differs by arm.

Clinical Protocol

Aim two anticipated results. We hypothesize that low doses of MMF will be well tolerated among healthy HIV-infected study participants who have fully ART-suppressed HIV. We hypothesize that the incidence of opportunistic infections will not exceed that of comparable larger cohorts of HIV-treated patients. Of note, certain opportunistic infections such as herpes zoster or HSV-2 recurrence continue to occur despite suppressive ART, while pneumocystis pneumonia, CMV end organ disease, cryptococcus and many other opportunistic infections are much less common in this context. Therefore, in the event of an infection, we will confer with the DSM panel to discuss whether any event is directly attributable to MMF. Additionally, we hypothesize that peripheral blood CD4+ and CD8+ T cell counts will remain unchanged throughout MMF therapy, and that HIV replication will remain well controlled on ART with the addition of MMF.

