3.0 STUDY DESIGN

This is an open-label, randomized Phase II trial to determine whether MMF given over 22 months meaningfully decreases the size of the HIV reservoir.

At the University of Washington in Seattle, we will enroll 5 study participants who have been on ≥ 2 years of suppressive ART. Study participants will be followed closely for at least 22 months with safety labs and serial measurements of the HIV reservoir (specifically, cell-associated HIV DNA and mRNA (**ca-DNA & ca-RNA**), quantitative viral outgrowth assay (**QVOA**), and single copy plasma viral

Clinical Protocol

load (**scVL**)). A “go/no-go” decision will occur after 12 months based on pre-defined thresholds of reduction in the HIV reservoir measured with ca-DNA.

All participants will be offered enrollment in a sub-study in which an anoscopy with rectum biopsies is performed on 3 occasions to assess the reservoir in the gastrointestinal lymphatic tissue (**GALT**).

We will vaccinate study participants with the annual influenza vaccine and analyze their humoral response to this vaccine approximately one month later with a routine blood draw done in conjunction with a safety labs blood draw.

We hypothesize that low doses of MMF will be well tolerated among healthy HIV-infected study participants who have fully ART-suppressed HIV. We hypothesize that the incidence of opportunistic infections will not exceed that of comparable larger cohorts of HIV-treated patients. Of note, certain opportunistic infections such as herpes zoster or HSV-2 recurrence continue to occur despite suppressive ART, while pneumocystis pneumonia, CMV end organ disease, cryptococcus and many other opportunistic infections are much less common in this context. Therefore, in the event of an infection, we will confer with the data safety management (DSM) panel to discuss whether this event is directly attributable to MMF. Finally, we hypothesize that peripheral blood CD4+ and CD8+ T cell counts will remain unchanged throughout MMF therapy, and that HIV replication will remain controlled on ART with addition of MMF.

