We hypothesize at least a 0.25-log reduction in cell-associated HIV DNA at one-year intervals in study participants who have a demonstrated anti-proliferative response to MMF treatment. We hypothesize that cell-associated HIV DNA will undergo a shift from predominant residence in T_{CM} and T_{EM} to predominant residence in T_N and T_{SCM} . In regards to our sub-study, we predict that reservoir depletion will occur with equivalent rates in blood and GALT.

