4.0 SELECTION AND ENROLLMENT OF SUBJECTS

4.1 Inclusion Criteria

- a. Confirmed HIV infection, by two different positive antibody tests and/or detectable plasma HIV RNA on two different dates
- b. ≥ 18 and ≤ 65 years of age
- c. Continuous ART during the last two years, with current ART preferably including an integrase inhibitor
- d. HIV RNA <40 copies / mL on four occasions during continuous ART of ≥ 2 years with no more than one blip of <1000 HIV RNA copies / mL
- e. CD4+ T cell count $> 350/\text{mm}^3$ within the past 365 days
- f. Karnofsky score ≥ 80
- g. Plan to reside in area 2 years
- h. Consents to study
- i. “Step 1” lead-in phase: Tolerability of MMF during one week dose escalation of 500 mg once daily (or Myfortic \odot 360 mg once daily)

Clinical Protocol

- j. "Step 2a" lead-in phase: Demonstrated tolerability and anti-proliferative effect (>= 80% anti-proliferative effect) of one week of MMF 500 mg twice daily (or Myfortic[®] 360 mg twice daily)
- k. "Step 2b" lead-in phase (only if necessary based on inadequate anti-proliferative effect on 500 mg bid): Demonstrated tolerability and anti-proliferative effect (>= 80% anti-proliferative effect) of one week of MMF 750 mg twice daily (or Myfortic[®] 540 mg twice daily)

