8.0 STATISTICAL CONSIDERATIONS

8.1 General Design Issues

This study intends to evaluate the effects of the FDA-approved drug, mycophenolate mofetil to determine if it diminishes the size of the HIV reservoir in participants on chronic ART. The study is a single-site, prospective, open label, and observational trial. We aim to enroll 5 participants on MMF 500 mg twice daily. Inclusion criteria are described above. In addition, we will screen each participant to ensure that they have a pharmacologic anti-proliferative response to MMF. The drug intervention

Clinical Protocol

will last a maximum of 22 months with possibility for study extension in participants tolerating drug who demonstrate continued reservoir reduction at 22 months but still have a detectable reservoir. Participants will be followed closely with serial safety lab measurements and clinical visits to ensure drug tolerability and safety. In addition, we will ensure that HIV viral load remains suppressed. Moreover, participants will have serial measurements of their HIV DNA reservoir using various assays. In order to remain enrolled in the MMF treatment arm of the study, participants will be required to show sequential 0.25 log reductions in the HIV reservoir at month 12. We will also include a sub-study in which participants undergo an anoscopy to measure the HIV reservoir in tissue rather than blood.

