8.2 Statistical outcomes

8.2.1 Main statistical outcome

- Change in cell-associated HIV DNA (ca-DNA) reservoir size as measured by multiplexed digital droplet PCR in study participants on versus off MMF (historical controls).

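### Section 8.6 names log viral load for the descriptive reservoir slopes and no outcome for the mixed model, so ca-DNA has no written model; the composition model also leaves out T_SCM

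*Combined protocol and SAP*

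**What the plan says.** Section 8.6 opens its analysis paragraph with "We will compute the change in reservoir volume in two ways".

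- **First analysis, labelled descriptive:** "we will use individual linear regressions to compute a slope in log viral load", abbreviated VL, with time as the only covariate. The slopes are summarised by their mean and standard deviation.
- **Second analysis:** a linear mixed model with a random intercept and slope per person. Its time-by-arm term is meant to show whether the reservoir falls faster on ART plus MMF than on ART alone in historical controls. No assay is named.
- **Composition:** a generalized linear mixed model whose only outcome is the naive (T_N) proportion of cells.

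Elsewhere the reservoir measure is explicit. Section 8.2.1 gives the main statistical outcome as "Change in cell-associated HIV DNA (ca-DNA) reservoir size as measured by multiplexed digital droplet PCR". Section 3.0 makes the month-12 decision "based on pre-defined thresholds of reduction in the HIV reservoir measured with ca-DNA" and states the effect as "We hypothesize at least a 0.25-log reduction in cell-associated HIV DNA at one-year intervals".

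Viral load has a different role in most places. Section 8.2.2 lists single copy viral load (scVL) as secondary and describes it as a measure of replication, and 8.2.3 groups plasma RNA with the safety measures. Entry requires "HIV RNA <40 copies / mL on four occasions during continuous ART" (4.1d). Section 3.0 expects that "HIV replication will remain controlled on ART with addition of MMF", and 8.1 says "we will ensure that HIV viral load remains suppressed". On the other hand, 3.0 also lists scVL among the serial reservoir measurements, and 2.2b places it under primary outcomes.

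**The concern.** Section 8.6 is the only place where the slope models are described. Read as written, it attaches viral load to the first model and nothing to the second. An analyst then has to decide which assay the main slope analysis uses. Several candidates are available: ca-DNA, ca-RNA, QVOA and scVL are all collected, 2.2 lists more than one of them as primary, and the endpoint row of Table 1 says only reservoir size. With five participants and no concurrent control (8.3), an outcome left open can be settled after the results are known.

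If viral load were used, the variable would be one that ART is expected to hold down whether or not the reservoir shrinks. The rationale in Section 1.2 itself separates persistence of latent cells from active replication.

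The composition outcome has a similar gap. Hypothesis 2.1e, Section 3.0 and Section 8.6 all predict movement of HIV DNA into two subsets, T_N and T_SCM, and only T_N is modelled.

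**Working it through.** **1. The plan's own figure.** Section 8.4.1 gives a decline on ART alone of 0.0068 log10 IUPM per month, with SD 0.017.
- Annual decline: 12 × 0.0068 = 0.0816 log10 (plan: 0.082).
- Percentage: 1 − 10^(−0.0816) = 17.1% (plan: 17%).
- Annualised SD: 12 × 0.017 = 0.204 (plan: 0.2).

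The figures reproduce. They are in IUPM, an outgrowth-assay unit, which is neither viral load nor ca-DNA.

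**2. The hypothesised effect (3.0), in ca-DNA.**
- Rate: 0.25 / 12 = 0.0208 log10 per month.
- Percentage: 1 − 10^(−0.25) = 1 − 0.562 = 43.8%.

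**3. Outcome by place in the document.**

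| Place | Outcome named |
|---|---|
| 8.2.1 main statistical outcome | ca-DNA |
| 3.0 go/no-go | ca-DNA |
| 3.0 0.25-log hypothesis | ca-DNA |
| 8.4.1 historical rates | log10 IUPM |
| 8.6 individual regressions | log viral load |
| 8.6 mixed model | none |

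The abbreviation list defines VL as viral load and has a separate entry for ca-DNA. Nothing redefines VL as a general reservoir measure. Section 8.6 mentions cell-associated DNA only in the composition hypothesis. So the main statistical outcome has no model that names it.

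**4. Consequence for the historical comparison.** A time-by-arm term needs treated and control data on one scale. The documents identify no ca-DNA control data, and the two historical rates in 8.4.1 (0.0068 and 0.0072 per month) are both in log10 IUPM. Naming ca-DNA therefore leaves open whether the interaction can be estimated for it.

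**5. Composition.** The documents give no subset shares, so these are assumed, to show the range only. Each starts with T_N and T_SCM at 5% each.

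| Assumed end shares | T_N ratio | T_N + T_SCM ratio |
|---|---|---|
| T_N 5%, T_SCM 50% | 5/5 = 1.0 | 55/10 = 5.5 |
| T_N 10%, T_SCM 45% | 10/5 = 2.0 | 55/10 = 5.5 |
| T_N 30%, T_SCM 30% | 30/5 = 6.0 | 60/10 = 6.0 |

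A T_N-only outcome is adequate when both subsets rise together. It shows no change when the shift goes wholly to T_SCM, although that shift would fit the hypothesis.

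**The case against.** The best defence is that context largely settles the label. The paragraph is about the reservoir, 8.2.1 fixes the main outcome as ca-DNA, and viral load is named only for the analysis labelled descriptive. The mixed model is aimed at the reservoir. The protocol also does not treat scVL as foreign to reservoir measurement, since 3.0 and 2.2b include it. VL is quite possibly a slip.

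Much of this stands, and it limits the point to an unspecified and inconsistently labelled outcome. It does not remove it: no text corrects the label, 2.2 and 8.2.2 disagree on whether scVL is primary, and Table 2 collects both low-level viral load and ca-DNA, so the literal analysis could be run without any missing data to expose the error.

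A reader might go further and infer that the plan fits all its reservoir slopes to plasma viral load and would miss the whole effect. On that reading, values below 40 copies/mL are not quantified, the viral load slope is 0, and all 0.25 log10 is lost. The documents do not support this. The 40 copies/mL figure is an entry criterion, not a stated limit of the study assay, and Table 2 schedules a low-level assay. If VL means scVL and scVL is assumed to fall by 0 to 0.25 log10, the part missed runs from 0.25 down to 0, which is no estimate. ca-DNA is also measured serially, so a fall would be seen in the data even if the written slope analysis did not use it.

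It is also fair that composition is a separate, smaller matter: 8.2.2 makes it a secondary statistical outcome.

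**Conclusion.** The point holds as a specification defect that should be corrected before analysis. Section 8.6 names viral load for the descriptive slopes and nothing for the mixed model, so ca-DNA has no model written for it. A viral load slope need not track a fall in ca-DNA, because the protocol expects viral load to stay controlled on ART in any case. The size of the loss cannot be quantified: the documents give neither an scVL limit nor an expected scVL decline. The month-12 go/no-go is unaffected, because 3.0 already bases it on ca-DNA. No power or sample-size figure changes, since none is stated.

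The composition gap also holds: one of the two hypothesised destination subsets is outside the modelled outcome. Its size is unknown without subset shares.

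**What to change.** In Section 8.6:

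- Name log10 ca-DNA as the outcome of both the individual regressions and the linear mixed model.
- Analyse scVL, ca-RNA and QVOA in separate secondary models.
- Define the composition outcome as the share of HIV DNA found in T_N plus T_SCM, or model each subset.
- Compare with historical controls only on the same assay scale. If no ca-DNA control data are available, report the ca-DNA slope within participants and limit the IUPM comparison to QVOA.

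**Cost.** The outcome changes are small wording edits. Table 2 already includes blood for ca-DNA by droplet digital PCR, so the slope correction needs no new sampling. The laboratory should confirm that HIV DNA is measured in T_SCM separately, as the stated hypothesis already requires. The real cost may be in the comparison: without ca-DNA control data there would be no formal historical comparison for the main outcome, and the plan should say so.

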Limited Interview/Limited PE		X	X	X		
Limited Interview only (no PE)						
Discussion of MMF side effects	X	X				
Obtaining consent	X					
MMF Drug 500mg MMF for the first week, then go up to 2x500mg for the second week			Dispense x1 week	Dispense x2 weeks		Dispense x2 wks or x5 wks
Urine PG---all visits with safety labs	0	0	0	0		0
PT/PTT (Pre-BIOP safety) blue	4.5					
CBC & Diff Lavender Hemogard Tube)	3	3	3	3		3
Comp Panel (3.5mL SST)	3.5	3.5	3.5	3.5		3.5
CD4/CD8 (Lavender Top Tube)	4	4	4	4		4
MMF Levels (at HMC) (3.5mL SST)		3.5		3.5	3.5	
HCABX & HBSAGX (only-as needed) (5mL SST)	5					
TB IGRA (only-as needed) (3 Quantiferon-TB Gold Tubes 1 mL each	3					
Low Level VL Assay (10mL EDTA)		0				20
QVOA		100				
Anti-Proliferation Assay (3.5mL SST)		7		3.5	3.5	
8.5mL Yellow ACD tubes for Anti Proliferation Assays, FACS for Ki67, TREC level PCR, Cell-associated DNA and mRNA ddPCR, PBMC and plasma banking			85	8.5	8.5	
2.5 mL PAXgene Blood RNA Tube for [name] Lab		5		5		2.5
MLs	23	211	10.5	31	15.5	142
Rolling volumes/8 weeks (max 450mL)		234.0	244.5	275.5	291.0	291
TEAspoons	4.7	42.8	2.1	6.3	3.1	433.0
TABLEspoons	1.6	14.3	0.7	2.1	1.0	448.5
						0.0
						28.8
						3.1
						0.0
						9.6
						1.0
Eligibility	Entry	week 1	week 2 T	week 2 P	week 3	week 4 T
						week 4 P

Phone call to stop MMF in case of lacking efficacy by anti-proliferation test

Clinical Protocol

BIOP						
week 60	wk 74 T	wk 74 P	wk 88 T	wk 88 P	week 90	
Mo. 15	Mo. 18.5	Mo. 18.5	Mo. 22	Mo. 22	Mo. 22.5	ConVF
						PreDC
X	X		X			X
R	R					
0	0		0		0	0
3	3		3		3	3
3.5	3.5		3.5		3.5	3.5
4	4		4		4	4
3.5	3.5	3.5	3.5	3.5	3.5	
20	20		0		20	20
			100			
3.5	3.5	3.5	3.5	3.5		
212.5	212.5	8.5	119	8.5		
5	5		5			
255	255	15.5	241.5	15.5	14	20
255.0	255.0	270.5	241.5	257.0	271.0	
51.7	51.7	3.1	49.0	3.1	2.8	4.1
17.2	17.2	1.0	16.3	1.0	0.9	1.4
week 60	week 74	week 74	week 88	week 88	week 90	

The bottom row in red indicates rolling blood volumes over 8 weeks prior to and including each blood draw and should not be higher than a total of 450 mL as per University of Washington policy.

Clinical Protocol

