2.0 STUDY HYPOTHESES AND OBJECTIVES

2.1 Hypotheses

- 2.1a MMF or Myfortic[©] will be well tolerated and will not decrease adherence to or antiviral efficacy of ART.
- 2.1b Peripheral CD4+ T-cell counts and percentages will not meaningfully decrease during treatment with MMF or Myfortic[©] and ART.
- 2.1c There will be no excess risk of opportunistic infections in MMF or Myfortic[©] treated study participants.
- 2.1d MMF or Myfortic[©] therapy will lead to a progressive decrease in reservoir size over 22 months of treatment.

Clinical Protocol

- 2.1e MMF or Myfortic[©] therapy will lead to a continual shift in HIV reservoir composition from primarily effector memory CD4+ T-cells (T_{em}) and central memory CD4+ T-cells (T_{cm}), to primarily stem cell like memory (T_{scm}) and naïve (T_n) CD4+ T-cells.
- 2.1f MMF or Myfortic[©] will eliminate detectable measures of the HIV reservoir, including cell-associated DNA/mRNA, and quantitative viral outgrowth.
- 2.1g MMF or Myfortic[©] will not decrease the humoral immune response to routine annual influenza vaccination.

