8.2.2 Secondary statistical outcomes

- Change in HIV replication by single copy viral load (scVL) in study participants on versus off MMF (historical controls).
- Change of viral reactivation by cell-associated HIV mRNA in study participants on versus off MMF (historical controls).
- Change of the inducible HIV reservoir size by quantitative viral outgrowth assay (QVOA) in study participants on versus off MMF (historical controls).
- Change of the cellular composition of the HIV DNA reservoir in study participants on versus off MMF (historical controls).
- CD4+ T cell numbers that recently emigrated from the thymus
- Blood CD4+ T cell count
- Complete blood cell count, comprehensive metabolic panel
- Incidence of opportunistic infection
- Antibody response to annual influenza vaccination

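### The plan expects reservoir measures to become undetectable, but the log-scale slope analyses in 8.6 have no way to use a non-detect and no analysis is given for hypothesis 2.1f

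*Combined protocol and SAP*

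**What the plan says.** Hypothesis 2.1f (section 2.1) states that the drug "will eliminate detectable measures of the HIV reservoir, including cell-associated DNA/mRNA, and quantitative viral outgrowth". Table 1 of the Protocol Summary lists the same hypothesis under the primary objective. Section 8.1 allows extension beyond 22 months only where the reservoir is still detectable, so the plan foresees participants in whom it is not.

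The main statistical outcome (8.2.1) is "Change in cell-associated HIV DNA (ca-DNA) reservoir size as measured by multiplexed digital droplet PCR". Single copy viral load (scVL), cell-associated mRNA and viral outgrowth (QVOA) are secondary (8.2.2).

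Section 8.6 computes reservoir change in two ways:

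- Descriptively, "we will use individual linear regressions to compute a slope in log viral load" for each participant, with time as the only covariate. I read the log outcome as the log of whichever reservoir measure is analysed.
- By linear mixed effects models "to estimate an average slope using all the data at once, and a random intercept and slope per person", with a time-by-arm interaction against historical controls. The scale is not stated. The log10 rates in 8.4.1 and the 0.25 log hypothesis imply it.

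For composition only, 8.6 will "include the proportion of cells that are naive (T_N) as the outcome in a generalized linear mixed model with a log link".

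The documents give no detection limit for any reservoir assay, no rule for zero or undetectable values, no censored or count model for reservoir size, and no analysis of the number of participants who become undetectable.

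**The concern.** The outcome that the plan hopes for is the one that its slope models cannot process. A result with no positive droplets, wells or plasma copies has no logarithm, so the analyst must drop it or substitute a value, and nothing fixes that choice in advance. With five participants, the choice can move the average slope materially, and it can do so in strong responders, whose later values are the ones that vanish.

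Two conclusions are exposed. One is the reservoir slope and its comparison with historical controls. The other is 2.1f itself: with no analysis attached, a non-detect could be reported as elimination when it shows only that nothing was found in the cells assayed.

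**Working it through.** **The plan's own figures.** From 8.4.1, 12 × 0.0068 = 0.0816 log10 per year on ART alone, and 1 − 10^(−0.0816) = 17.1%. The plan states 0.082 and 17%. Its annualised SD is 12 × 0.017 = 0.204 (stated 0.2). The half-life is log10(2)/0.0068 = 44.3 months (44 in section 1.2). All reproduce, but none bears on non-detects.

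**Planned effect.** Over 22 months, 0.25 log10 per year gives 0.25 × 22/12 = 0.46 log10, a 2.9-fold fall. Few values would be lost unless baseline lies within about 0.5 log10 of the limit.

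**Count simulation.** Assumptions, none from the documents: 16 visits over 22 months; Poisson counts with mean λ0 × 10^(−s·t), where λ0 is the baseline count, s the yearly log10 fall and t time in years. The expected count at month 22 is λ0 × 10^(−s × 22/12). Estimated falls are in log10 per year. Ranges cover separate runs, and a dash means not reported.

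| λ0 | True s | Expected count, month 22 | Zeros set to 1 | Zeros dropped | Poisson regression |
|---|---|---|---|---|---|
| 20 | 0.25 | 7.0 | bias about 0.02 or less | bias about 0.02 or less | – |
| 20 | 0.5 | 2.4 | 0.53 | 0.52 | – |
| 20 | 1.0 | 0.29 | 0.77–0.79 | 0.86–0.87 | 1.00–1.01 |
| 20 | 1.5 | 0.04 | 0.67–0.79 | 1.06–1.22 | 1.50–1.53 |
| 5 | 0.5 | 0.61 | 0.34–0.37 | 0.33–0.36 | 0.51–0.52 |
| 100 | 1.0 | 1.5 | 1.02 | 1.00 | – |
| 200 | 1.0 | 2.9 | 1.03 | 1.03 | – |

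Attenuation appears in the rows where the expected count falls below about one during follow-up. Visit times are assumed, and they matter: at true 1.5 the runs differ by 0.79 − 0.67 = 0.12 and 1.22 − 1.06 = 0.16.

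**Censored log-normal simulation.** Assumptions: 10 visits, residual SD 0.15 log10, baseline a stated distance above the limit. Median estimated falls, log10 per year:

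| Baseline above limit | True | Set to limit | Dropped | Set 1 log below limit | Censored (Tobit) fit |
|---|---|---|---|---|---|
| 0.5 | 0.25 | 0.23 | 0.21 | 0.43 | 0.25 |
| 0.5 | 0.5 | 0.30 | 0.38 | 0.95 | 0.50 |
| 0.5 | 1.0 | 0.25 | 0.83 | 0.93 | 1.05 |
| 0.5 | 2.0 | 0.19 | 1.67 | 0.75 | 1.93 |
| 1.0 | 0.25 | 0.25 | 0.25 | 0.25 | 0.25 |
| 1.0 | 1.0 | 0.60 | 0.90 | 1.27 | 0.99 |
| 0.3 | 2.0 | 0.09 | 1.14 | 0.48 | 1.40 |

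With baseline 0.5 log10 above the limit and non-detects set to the limit, a true 2.0 is estimated as 0.19, below the 0.23 estimated for a true 0.25, so the order of responders reverses. Dropping non-detects keeps the order and loses 16% to 24%. A low substitute can overstate the fall: 0.95 for a true 0.5.

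**Which outcomes are exposed.** Section 4.1 requires "HIV RNA <40 copies / mL on four occasions during continuous ART", so single-copy results may include zeros from baseline. QVOA is a limiting-dilution count. Steep falls lie within the plan's own rationale: section 1.2 cites a study in which half of six participants had QVOA reductions of 1 to 2 orders of magnitude after 20 weeks of the drug.

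**The case against.** The strongest reply is that the main outcome may hardly be affected. At the hypothesised 0.25 log10 with reasonable counts the bias is negligible, and at 1.0 log10 per year it disappears with 100 or more baseline counts. The documents give no counts or detection limits, so no one can show that ca-DNA is at risk. This stands, and it limits the point to low-count assays and steep declines.

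Four stronger readings are tempting, and the documents do not support them.

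- A reader might infer that log regression is the only analysis stated. Section 8.6 also gives a linear mixed model, which carries the comparison with controls, and a log-link model for composition. Neither deals with a zero in reservoir size.
- A reader might infer that log regression always flattens the best responders. The direction and size depend on the missing non-detect rule, and a low substitute can steepen the slope.
- A reader might infer from the changing blood volumes in Table 2 that the ddPCR detection limit drifts in a harmful direction. The row concerned is shared: "8.5mL Yellow ACD tubes for Anti Proliferation Assays, FACS for Ki67, TREC level PCR, Cell-associated DNA and mRNA ddPCR", plus banking. Its total therefore does not give the ddPCR input. The legible late volumes (212.5 and 119 mL) also exceed the 85 mL at Entry, which would make later non-detects more informative.
- A reader might infer that count models must replace the planned ones. For historical controls, 8.4.1 gives only published log10 slopes, so a count model by arm may be impossible. Count regression can also fail with sparse data: with 5 baseline counts and 8 visits, a true 1.5 gave a mean of 2.13.

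**Conclusion.** The concern holds in a limited form. The plan foresees undetectable values, its reservoir slope models cannot use them, and 2.1f has no analysis. This is more than a missing detail, because a likelihood that uses non-detects is available at small cost.

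Under an assumed 20 counts at baseline, a true 1.5 log10 per year is estimated as about 0.7 to 0.8 or 1.1 to 1.2, depending on the rule. With 5 counts, a true 0.5 becomes about 0.35 under either rule. At 0.25 log10 per year with 20 or more counts, or 1.0 with 100 or more, there is no material bias. These sizes rest on assumed counts, visit times, residual variation and distances from the limit. The absence of a rule and of an analysis for 2.1f rests on the text alone.

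**What to change.** In 8.6:

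1. State each assay's detection limit and fit the reservoir slopes with a likelihood that uses non-detects. A left-censored (Tobit-type) linear mixed model with the assay- and sample-specific limit is enough. Where raw counts and assay input exist, a Poisson or negative binomial model with log cells or log plasma volume assayed as offset is an alternative, with a limiting-dilution likelihood for QVOA.
2. Apply the same non-detect rule to historical controls. Where only published control slopes are available, compare the MMF slope with those.
3. For 2.1f, report how many of the five participants are undetectable, assay by assay. Describe each non-detect as below detection in N cells, with a one-sided 95% upper bound of about 3/N (−ln 0.05 = 3.0), and not as elimination.

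The cost is SAP wording and slightly more analysis work, with no new samples or visits. Estimates will be less stable where few values are detectable: the censored fit gave 1.40 for a true 2.0 when baseline was only 0.3 log10 above the limit. QVOA needs particular care, since the legible part of Table 2 shows its 100 mL draw only at Entry and week 88.
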